8.3 Part 1 Dose Escalation Rules

Part 1 of the study followed a 3 + 3 dose escalation design to evaluate once-weekly (Schedule A) administration of modakafusp alfa for DLTs and to determine the MTD/OBD for further assessment in phase 2. A starting dose of 0.001 mg/kg was selected for Schedule A on the basis of a MABEL calculation (Section 4.6.1).

Patients were enrolled in cohorts of 3 and assessed for DLTs over a 28-day period (21 days for Schedule C) as detailed in Figure 8.a.

During Part 1, patients who missed one or more scheduled Cycle 1 doses of modakafusp alfa for reasons other than a DLT were to be replaced.

Details regarding the management of dose escalation decisions can be found in the Cohort Management Plan.

For the FIH evaluation of modakafusp alfa, a threshold of fatal AEs related to modakafusp alfa of 6% is proposed. Any rate of fatal events related to modakafusp alfa clearly in excess of this will result in the stopping of the trial. For the 30 patients expected to be treated at MTD/OBD between phase 1 and phase 2 with one specific dose and schedule, this means that the cohort will be stopped if 3 fatal AEs related to modakafusp alfa occur, or if 2 fatal AEs related to modakafusp alfa occur during the recruitment of the first 12 patients in each cohort.

The trial will also be stopped if the rate of modakafusp alfa—related Grade 4 events in any nonhematologic System Organ Class (SOC) exceeds 10% (with the exception of Grade 4 asymptomatic laboratory abnormalities). The trial will also be stopped if events meeting the criteria of a DLT occur with an incidence of greater than 40% at any point. The stop will result in an immediate halt in enrollment and may also necessitate the halting of treatment of ongoing patients, depending on the nature and severity of the safety risk. A final decision to terminate the study will be made only after a full review of the safety data by the sponsor's safety management team.

Figure 8.a is a diagrammatical representation of the dose escalation scheme.

[figure not shown]

Figure 8.a Dose Escalation Scheme

DLT: dose-limiting toxicity; MTD: maximum tolerated dose.

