8.2 Definitions of DLT

Toxicity will be evaluated according to the NCI CTCAE, Version 5.0.

Nonhematologic TEAEs of NCI CTCAE Grade ≥ 3 clearly unrelated to the underlying disease and occurring during the first cycle will be considered DLTs (see Section 10.2 for relatedness guidance), with the following exceptions:

- Asymptomatic laboratory changes (other than renal and hepatic laboratory values, and Grade 4 lipase/amylase) that can be successfully supplemented (reversion of Grade 4 events to Grade ≤2, reversion of Grade 3 events to Grade ≤1 or baseline) within 72 hours.
- Grade 3 nausea/vomiting that can be managed subsequently with antiemetics (Grade 3 nausea or vomiting that persists beyond 48 hours with or without appropriate medical intervention will be considered a DLT).
- Grade 3 fatigue lasting less than 72 hours.
- Grade 3 elevation of alanine aminotransferase (ALT) or aspartate aminotransferase (AST) that resolves to Grade ≤1 or baseline within 7 days.
- Grade 3 IRR that responds to symptomatic treatment, without recurrence of Grade 3 symptoms.

The following hematologic TEAEs Grade ≥3 clearly unrelated to the underlying disease and occurring during the first cycle will be considered DLTs:

- Grade \geq 3 hemolysis.
- Grade 4 neutropenia lasting more than 7 consecutive days.
- Grade 4 thrombocytopenia lasting more than 14 consecutive days.
- Grade 3 thrombocytopenia with clinically significant bleeding.
- Any other Grade ≥4 hematologic toxicity with the exception of Grade 4 lymphopenia.

An incomplete recovery from treatment-related toxicity causing a >2-week delay in the next scheduled infusion before the initiation of Cycle 2 will be considered a DLT.

In Part 1, DLTs are events meeting the criteria above that occur before Cycle 2 Day 1 administration. Related TEAEs meeting DLT definitions occurring in later cycles or in Phase 2 (DLT-like events) will determine the suitability of the MTD/OBD dose for future studies.

Dose and schedule modifications for toxicity are described in Section 8.4.

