8.4.2 Criteria for Beginning or Delaying a Subsequent Treatment Cycle

Treatment with modakafusp alfa will use a cycle length of 28 days (21 days for Schedule C). For a new cycle of treatment to begin, the patient must meet the following criteria:

- Absolute neutrophil count must be ≥1000/mm³. Granulocyte-colony stimulating factor (G-CSF) can be used to reach this level.
- Platelet count must be $\geq 50,000/\text{mm}^3$.

For therapy to resume, toxicity considered to be related to treatment with modakafusp alfa must have resolved to Grade ≤1 or baseline (Grade 2 for platelets), or to a level considered acceptable by the physician. If the patient fails to meet the above-cited criteria for retreatment, initiation of the next cycle of treatment should be delayed for 1 week. At the end of that week, the patient should be re-evaluated to determine whether the criteria for retreatment criteria have been met. If modakafusp alfa cannot be administered as scheduled, the patient can continue taking the weekly dexamethasone doses unless the investigator considers that it is in the patient's best interest to also hold dexamethasone.

If there is a delay of a subsequent cycle longer than 2 weeks because of a related AE, the patient may be withdrawn from treatment unless there is clinical benefit as assessed by the investigator, with agreement by the sponsor. Modakafusp alfa dosing may be continued at the previously established safe dose level or below.

For modakafusp alfa infusions within the same cycle (Schedules A and B [once every 2 weeks (Q2W)]), the decision to hold treatment is left to investigator discretion based on clinical and analytical data and based on the toxicity that the patient presented with previous infusions in the same cycle. The investigator should differentiate from acute toxicity (eg, an IRR) from which the patient has recovered at the time of the next infusion or subacute toxicity (eg, neutropenia) that might worsen with another infusion if it is not in a clear recovery path. If the dose cannot be administered on the scheduled day, the patient can be reviewed at the investigator's discretion in the following 48 hours. If modakafusp alfa cannot be administered within a cycle in this 48-hour window, the dose will be missed and the patient scheduled for the next administration per the schedule of events (SOE).

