9.4.1 Discontinuation of Treatment with Study Drug and Patient Replacement

Study drug must be permanently discontinued for patients meeting any of the following criteria:

• Patient experiences an AE or other medical condition that indicates to the investigator that continued participation is not in the best interest of the patient.

Treatment with study drug may also be discontinued for any of the following reasons:

- AE.
- Complete 1 year of treatment (unless exception is granted by the sponsor) in Parts 1 and 2 only.
- Protocol deviation (after discussion with sponsor).
- Progressive disease (if the investigator considers that treatment after PD is in the patient's best interest, it can be approved after consultation with the sponsor).
- Symptomatic deterioration.
- Unsatisfactory therapeutic response.

- Study terminated by sponsor.
- Withdrawal by subject.
- Female patient has confirmed pregnancy.
- Lost to follow-up.
- Other.

Once study drug has been discontinued, all study procedures outlined for the EOT visit will be completed as specified in the SOE (Appendix A). The primary reason for study drug discontinuation will be recorded on the eCRF.

In Part 1, patients who miss 1 or more modakafusp alfa infusions during Cycle 1 for reasons other than a DLT will be replaced. In Part 2 and Part 3, patients who receive 1 or more infusions of study drug will not be replaced.

Note that some patients may discontinue study drug for reasons other than PD before completing the full treatment course; these patients will remain in the study for posttreatment assessments as outlined in the SOE (Appendix A) until PD or withdrawal of consent.

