13.3 Determination of Sample Size

Part 1 of the study will follow a standard 3 + 3 dose escalation design. Under this design, the probability of dose escalation according to the true DLT rate is as follows:

True DLT rate	5%	10%	20%	30%	40%	50%	60%	70%
Probability of escalating	97%	91%	71%	49%	31%	17%	8%	3%

DLT: dose-limiting toxicity.

The probability of not observing a DLT in a sample size of 6 patients according to the true DLT rate is as follows:

True DLT rate	5%	10%	20%	30%	40%	50%	60%	70%
Probability of no toxicity	74%	53%	26%	12%	4.7%	1.6%	0.4%	<0.1%

DLT: dose-limiting toxicity.

Patients will be considered evaluable in Part 1 for MTD/OBD assessment provided they have not missed any of their infusions of modakafusp alfa in Cycle 1 and have not had a DLT. Patients who are not considered evaluable as defined above will be replaced.

Part 2 Expansion

The study will enroll up to 25 patients in each arm to further characterize safety of the OBD/MTD and obtain preliminary clinical efficacy data. An OBD/MTD dose will be considered clinically relevant if at least 11 out of 25 response evaluable patients have a confirmed PR or better. With a vague beta prior with shape parameters 0.428 and 1 for ORR (ie, mean of 30%), 11 responders out of 25 gives a greater than 90% posterior probability of true ORR being greater than 30%. The design has reasonable operating characteristics. With a true ORR of 30%, the probability of declaring success is 7%. In contrast, with a true ORR of 50%, the probability of declaring success is 70%.

Part 3 Extension

The primary objective of Part 3 of the study is to determine the confirmed ORR, including PR, VGPR, CR, and sCR assessed according to the IMWG criteria (Appendix F) to modakafusp alfa in patients with MM previously treated with ≥3 lines and with evidence of disease progression who are refractory to, or intolerant of, a PI, an IMiD, and an anti-CD38 mAb (triple refractory). The sample size was determined to claim that the true ORR is greater than the threshold response rate of 20% within each treatment arm. A total sample size of approximately 236 enrolled patients (118 patients per arm) will allow the study to have over 90% power to rule out an uninteresting response rate of 20% if the true rate is 35% with a 1-sided alpha of 0.025.

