7.2 Analysis Sets

Part 1 and Part 2

- Safety Analysis Set: The safety analysis set will include all enrolled patients who receive at least 1 dose of the study drug even an incomplete dose, of modakafusp alfa or Dexamethasone. The safety population will be used for safety related analyses such as AE, concomitant medications, laboratory tests, and vital signs. In addition, it will also be used for the efficacy analyses.
- Response-Evaluable Analysis Set: The subset of the safety analysis set of patients treated at the MTD/OBD from the Part 2 dose expansion cohorts with measurable disease at baseline and at least 1 post-treatment efficacy evaluation. The response-evaluable analysis set will be used in the futility analysis of the Part 2 expansion.
- DLT Evaluable Analysis Set: Patients who receive all Cycle 1 doses of modakafusp alfa or experience a DLT in Cycle 1 in the Part 1 dose escalation cohorts.
- Pharmacokinetic (PK) Analysis Set: The PK analysis set includes patients from the safety analysis set who have sufficient data to report at least 1 PK concentration for modakafusp alfa. The PK analysis set will be used for PK analysis.
- Immunogenicity-evaluable Analysis Set: The immunogenicity-evaluable analysis set will include patients from the safety analysis set with a baseline assessment and at least 1 post-baseline immunogenicity assessment. The immunogenicity-evaluable analysis set will be used for immunogenicity analysis.

Part 3

- Full Analysis Set (Safety Analysis Set): The full analysis set will include all enrolled patients who receive at least 1 dose of the study drug even an incomplete dose, of modakafusp alfa. The full analysis set will be used for baseline assessment, efficacy analysis and PRO compliance. The safety analysis set will be used for safety analysis.
- Intent-to-treat (ITT) Analysis Set: The ITT analysis set will include all randomized patients regardless of whether they receive study drug or adhere to the assigned dose. The ITT analysis set will be used for listings.
- Pharmacokinetic (PK) Analysis Set: The PK analysis set includes patients from the safety analysis set who have sufficient data to report at least 1 PK concentration for modakafusp alfa. The PK analysis set will be used for PK analysis.

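### The Part 1 DLT-evaluable definition sets no minimum observation time, so on single-dose Schedules C and D a patient lost early counts as DLT-free

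*Protocol*

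**What the plan says.** Protocol 8.3 enrols Part 1 patients in cohorts of three and sets a DLT assessment period of 28 days, or 21 days on Schedule C. On replacement it states that "patients who missed one or more scheduled Cycle 1 doses of modakafusp alfa for reasons other than a DLT were to be replaced". Section 9.4.1 repeats the rule for Part 1: "patients who miss 1 or more modakafusp alfa infusions during Cycle 1 for reasons other than a DLT will be replaced". SAP 7.2 defines the DLT Evaluable Analysis Set as "Patients who receive all Cycle 1 doses of modakafusp alfa or experience a DLT in Cycle 1 in the Part 1 dose escalation cohorts". None of these makes completion of the assessment period a condition.

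The documents also disagree on what a DLT does to evaluability. Protocol 13.3 calls a patient evaluable "provided they have not missed any of their infusions of modakafusp alfa in Cycle 1 and have not had a DLT", which read literally excludes patients with a DLT. SAP 6.0 makes a DLT an alternative route to being evaluable.

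Schedules C (every 3 weeks) and D (every 4 weeks) have a single infusion per cycle, on Day 1. Several DLTs in Protocol 8.2 need time to appear: Grade 4 neutropenia persisting beyond 7 days, Grade 4 thrombocytopenia persisting beyond 14 days, and incomplete recovery "causing a >2-week delay in the next scheduled infusion before the initiation of Cycle 2 will be considered a DLT".

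On Schedules A and B, Protocol 8.4.2 leaves within-cycle holds to the investigator and adds: "If modakafusp alfa cannot be administered within a cycle in this 48-hour window, the dose will be missed". Protocol 8.4.1 bars dose modification in Cycle 1 unless the patient has a DLT.

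**The concern.** With one dose per cycle, every treated patient on Schedules C and D meets the dose condition on Day 1. Someone who leaves observation a few days later without a DLT enters the denominator as a non-event, although the duration-based DLTs could not yet have been seen. The delay criterion needs more than 28 + 14 = 42 days after the first dose on Schedule D and more than 21 + 14 = 35 days on Schedule C.

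The DLT count by dose level is a Part 1 primary endpoint. It supports the 3 mg/kg Q4W MTD, from which the 240 mg arm of Part 3 was derived. The late DLTs concern this drug's main toxicity. Protocol 4.6.2 reports Grade 4 thrombocytopenia in 17% and Grade 4 neutropenia in 30%, and one of the two DLTs at 6 mg/kg was a Cycle 2 delay of more than 2 weeks.

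**Working it through.** **Inputs.** The 3+3 rule (SAP 6.0) escalates on 0 DLTs in 3 patients, or on 1 in 3 followed by 0 in 3. The stated escalation probabilities come from Protocol 13.3. The documents give no number of patients lost early, so the loss figures below are assumptions.

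**1. The plan's own table.** With true DLT rate p and q = 1 − p, P(escalate) = q³ + 3pq² × q³. For p = 5, 10, 20, 30, 40, 50, 60 and 70% this gives 97.3, 90.6, 70.9, 49.4, 30.9, 17.2, 8.2 and 3.2%. The stated row is 97, 91, 71, 49, 31, 17, 8 and 3%, so it reproduces. The formula assumes that every counted patient is fully observed.

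**2. One of the first three wholly unobserved but counted DLT-free; the next three fully observed.** P(escalate) = q² + 2pq × q³.

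| True rate | Calculation | Result | Plan |
|---|---|---|---|
| 30% | 0.49 + 0.42 × 0.343 | 63% | 49% |
| 40% | 0.36 + 0.48 × 0.216 | 46% | 31% |
| 50% | 0.25 + 0.50 × 0.125 | 31% | 17% |

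**3. Range for partial loss.** Let f be the share of patients lost and u the share of their DLTs that would fall after the loss. The observed rate is p(1 − fu), which never exceeds p. Putting it into the formula in step 1 for all cohorts gives:

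| f | u | True 30%: observed rate, P(escalate) | True 40%: observed rate, P(escalate) |
|---|---|---|---|
| none | – | 30%, 49% | 40%, 31% |
| 1/6 | 0.5 | 27.5%, 55% | 36.7%, 37% |
| 1/6 | 1 | 25%, 60% | 33.3%, 43% |
| 1/3 | 0.5 | 25%, 60% | 33.3%, 43% |
| 1/3 | 1 | 20%, 71% | 26.7%, 56% |

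The last row exceeds step 2 because it applies the loss to both cohorts.

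**4. What zero DLTs at the MTD can exclude.** Protocol 4.6.2 reports no DLTs at 3 mg/kg and mentions 7 Q4W patients there. I assume those 7 are the DLT denominator. The one-sided 95% upper bound is 1 − 0.05^(1/n): 34.8% if all 7 were fully observed, 39.3% if 6 were, 45.1% if 5 were.

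**5. Replacement on Schedules A and B.** Let h be the share replaced after a hold for toxicity short of a DLT, and r their full-dose DLT risk relative to p. The rate among those kept is (p − hrp)/(1 − h). At p = 30% and h = 20%:

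| r | Rate among those kept | P(escalate) |
|---|---|---|
| 0.5 | 33.8% | 42% |
| 1 | 30% | 49% |
| 1.5 | 26.2% | 57% |
| 2 | 22.5% | 65% |

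The direction depends on r, which the documents do not give.

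**The case against.** The strongest reply is that leaving treatment is not leaving observation. Protocol 10.3 collects AEs for 30 days after the last dose unless new anticancer therapy starts, and SAEs for those 30 days even then. After a single Day 1 dose this spans the 28- or 21-day period. An end-of-treatment visit with hematology follows, and Section 9.4.1 keeps patients who stop for reasons other than progression in post-treatment assessment. This stands, and it narrows the exposure to withdrawal, loss to follow-up and early new therapy. A residue remains even for followed patients: blood counts may be less frequent, and the Cycle 2 delay criterion cannot be judged if no further infusion is planned.

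It also stands that no affected patient is documented, that the delay DLT at 6 mg/kg was captured, and that Protocol 8.3 refers escalation decisions to a Cohort Management Plan not among these documents. That plan may require follow-up, but the SAP analysis set would still omit it.

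A reader might go further in two ways. One is to infer that evaluability rests on doses alone. It does not: under SAP 7.2 a Cycle 1 DLT also qualifies. The other is to infer that replacing Schedule A and B patients whose dose was held must also understate the DLT rate. Step 5 shows that this requires held patients to have above-average DLT risk. That is plausible, since 8.4.2 speaks of toxicity that another infusion might worsen, but it is not established. Nor can those holds bear on the Q4W MTD, where Cycle 1 has one dose.

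**Conclusion.** The point holds for Schedules C and D. As written, the evaluability rule counts an incompletely observed patient without a DLT as DLT-free, and the resulting bias can only be downward. If one of the first three patients is wholly unobserved, escalation probability rises by about 14 to 15 percentage points at true DLT rates of 30% to 50%. Partial observation gives smaller shifts, and none arises if every counted patient completed the period. The actual size is unknown because the number affected is not given. The documents do not show that the 3 mg/kg MTD is wrong; they leave open how many patients its zero-DLT result rests on.

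For Schedules A and B, the supported conclusion is only that patients replaced after a hold for sub-DLT toxicity should be visible in the report. The conflict between Protocol 13.3 and the SAP over patients with a DLT is a separate, plain inconsistency.

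**What to change.** - In SAP 7.2 and 6.0 and Protocol 13.3, define DLT-evaluable as having had a Cycle 1 DLT, or having received all Cycle 1 doses and been observed for the full DLT period. Unless Cycle 2 was given, that includes enough follow-up to judge the delay criterion. This wording also removes the conflict between 13.3 and the SAP.
- Re-derive the flag from data already collected, report DLTs by dose level on this set, and list the counted patients who did not complete the period.
- For Schedules A and B, list patients replaced after a dose was missed for drug-related toxicity short of a DLT. Show the DLT rate both excluding them and counting them as events. Returning them to the denominator as non-events would lower the rate further: in step 5 with r = 2, 0.8 × 22.5% = 18%.
- Reconcile Protocol 8.4.1 and 8.4.2 on Cycle 1 dose holds.

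The cost is wording, one analysis-set flag and two short listings. A few denominators may shrink. Because escalation has concluded, past escalation decisions do not change; what changes is how the DLT results and the MTD are reported and read.

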8.4 Dose Modification Guidelines

Dose modification guidelines for toxicities are described below for modakafusp alfa on the basis of the type and severity of AEs and causality determination by investigators. Further clarification can be obtained in consultation with the sponsor clinician (or designee).

8.4.1 Part 1 Dose Escalation

Although DLTs may occur at any point during treatment, only DLTs occurring during Cycle 1 influenced decisions regarding dose escalation, expansion of a dose level, or evaluation of intermediate dose levels. Dose modifications were not permitted during Cycle 1 of therapy

unless the patient experiences a DLT. DLTs are defined in Section 8.2. Patients were to be evaluated at least weekly for possible toxicities that may have occurred after the previous dose(s). Toxicities are to be assessed according to the NCI CTCAE, Version 5.

If multiple toxicities were noted, the dose adjustments and/or delays were to be made according to the AE with the highest toxicity grade, and the same dose modification guidelines were to apply to subsequent cycles unless otherwise noted.

8.4.2 Criteria for Beginning or Delaying a Subsequent Treatment Cycle

Treatment with modakafusp alfa will use a cycle length of 28 days (21 days for Schedule C). For a new cycle of treatment to begin, the patient must meet the following criteria:

- Absolute neutrophil count must be ≥1000/mm³. Granulocyte-colony stimulating factor (G-CSF) can be used to reach this level.
- Platelet count must be $\geq 50,000/\text{mm}^3$.

For therapy to resume, toxicity considered to be related to treatment with modakafusp alfa must have resolved to Grade ≤1 or baseline (Grade 2 for platelets), or to a level considered acceptable by the physician. If the patient fails to meet the above-cited criteria for retreatment, initiation of the next cycle of treatment should be delayed for 1 week. At the end of that week, the patient should be re-evaluated to determine whether the criteria for retreatment criteria have been met. If modakafusp alfa cannot be administered as scheduled, the patient can continue taking the weekly dexamethasone doses unless the investigator considers that it is in the patient's best interest to also hold dexamethasone.

If there is a delay of a subsequent cycle longer than 2 weeks because of a related AE, the patient may be withdrawn from treatment unless there is clinical benefit as assessed by the investigator, with agreement by the sponsor. Modakafusp alfa dosing may be continued at the previously established safe dose level or below.

For modakafusp alfa infusions within the same cycle (Schedules A and B [once every 2 weeks (Q2W)]), the decision to hold treatment is left to investigator discretion based on clinical and analytical data and based on the toxicity that the patient presented with previous infusions in the same cycle. The investigator should differentiate from acute toxicity (eg, an IRR) from which the patient has recovered at the time of the next infusion or subacute toxicity (eg, neutropenia) that might worsen with another infusion if it is not in a clear recovery path. If the dose cannot be administered on the scheduled day, the patient can be reviewed at the investigator's discretion in the following 48 hours. If modakafusp alfa cannot be administered within a cycle in this 48-hour window, the dose will be missed and the patient scheduled for the next administration per the schedule of events (SOE).

